#### Missing Data

Censoring will be assumed to be noninformative (i.e., the distribution of censoring times is independent of event times, conditional on the set of observed covariates). Missing data will be described in detail, including comparisons among participants that remained in the study to those that dropped out across demographic and outcome variables using t-tests, Little's MCAR test, or logistic regression (Nicholson, Deboeck, & Howard, 2015). Sensitivity analyses will be used to gauge the stability of inferences (Enders, 2010). When possible, we will use full-information maximum likelihood (FIML) estimation under the MAR missing data assumption (corresponding to the assumption of noninformative right

censoring) estimation option in the Mplus 7.3 software program to deal with missing data related to censoring and time-varying covariates with measurement intervals that do not correspond to the precision with which event times are measured. When appropriate, the robust standard error option, and the corresponding Satorra-Bentler correction for chi-square difference tests to evaluate site-level difference, will be used to correct for non-normality (Muthén & Masyn, 2005; Singer & Willett, 2003; Wang & Wang, 2012).

#### 4.4.2.1. Hypothesis 1.

##### Approach

To evaluate this hypothesis, we will use a discrete time survival analysis (DTSA) within the structural equation modeling (SEM) framework (Muthén & Masyn, 2005; Raykov, Gorelick, Zajacova, & Marcoulides, 2017). This approach offers substantively important extensions to conventional DTSA models (e.g., logistic regression) that more accurately reflects the complexity and interconnectedness of survival (i.e., event history modeling) processes (Masyn, 2014). This more general approach includes the ability to model unobserved population heterogeneity (frailty) in the event history process, latent variable predictors of event history (e.g., health-related quality of life) including possible mediators and moderators, recurring events, competing risks, parallel and sequential growth processes (i.e., between-person variability in within-person change over time), onset-to-growth models, parallel event history processes, measurement error on event occurrence, hazard risk set matching, handling multilevel data structures, and time-varying covariate effects (non-proportional hazard) among other advantages (Masyn, 2013, 2014). Figure 1 presents an exemplary DTSA within the context of SEM (simplified for ease of presentation). In this example, three binary indicators (1, event occurred; 0, event not occurred) corresponding to the  $j = 3$  proposed measurement occasions ( $e_j$ ). In this analysis the hazard probability for a given measurement occasion will be defined as the probability of mortality in that occasion, provided that patient is alive. The hazard probability will then be related to time-varying ( $w_j$ ) and time-invariant ( $x$ ) covariates through a logit link function to parameterize the effect of a particular covariate on the log hazard odds of mortality during a given time interval. We will then describe covariate effects in terms of a hazard odds ratio (hOR). For example, if clinical protocol is coded 1 for typical and 0 for being based on a shock severity score, were estimated to have a hOR of 2.0 at 30 days, we would note that the odds of mortality at 30 days for those without a shock severity protocol was twice the odds of mortality at 30 days for those with a shock severity protocol. This model can be written as:  $logit(Pr(e_j = 1)) = \alpha_j + \beta_j x + \gamma_j w_j$ , where  $\alpha_j$  is the log hazard odds (with all covariates set to 0),  $\beta_j$  is the difference in the log hazard odds and  $exp(\beta_j)$  is the hazard odds ratio (hOR) for a positive one unit difference in  $x$  (controlling for covariates  $w_j$ ), and  $\gamma_j$  represents a time-varying covariate effect for the difference in log hazard odds. The assessment of non-inferiority will be performed by comparing hazard odds ratio confidence intervals to the non-inferiority margin (Althunian, Boer, Groenwold, & Klungel, 2017). Specifically, since lower is better, non-inferiority will be concluded when the actual hazard ratio is less than the clinically acceptable ratio of 1.2.

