## **1. OBJECTIVES**

### **1.1. Hypotheses**

A standardized clinical protocol that selects patients for MCS based on shock severity, will be non-inferior with respect to 1 month and 1 year mortality, compared to standard clinical protocols that do not differentiate based on shock severity in adult patients following an initial diagnosis of acute myocardial infarction complicated by cardiogenic shock (AMICS).

Those patients with shock that is not severe and do not have MCS, have a mortality rate that is similar or better than patients who have severe shock and receive MCS.

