#### 4.1.1 Primary Outcome Variable

The primary outcome variable will be 30-day all cause mortality.

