#### 4.1.2 Secondary Outcome Variable(s)

Key secondary outcome variables for analysis may include but are not limited to:

- One year mortality
- length of ICU care
- requirement for renal replacement therapy
- dose and duration of catecholamine therapy

- requirement for implantation of an active LVAD or referral for cardiac transplantation
- time to support (arrival to tertiary facility to implantation)
- use of right heart catheterization
- Attainment of TIMI III flow post reperfusion
- Attainment of Cardiac power > 0.6 watts after completion of therapy
- Reduction or elimination of vasopressors and inotropic agents.
- blood products during admission
- hemolysis requiring device discontinuation
- vascular complication requiring surgery

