### 4.4 Statistical Analysis

**4.4.1. Exploratory analysis.** Variable distributions will be examined using summary measures, tables, and graphics, such as histograms and scatter plots, where appropriate. Variables will initially be used as they were obtained; however, transformation may be

necessary or prove more informative. For example, continuous variables may be categorized, using common category boundaries found in the literature or based on percentiles of the variable distribution, in order to stratify the data. Student's t-test or the Wilcoxon rank-sum and chi-square statistics will be used to examine simple associations. For event history outcomes, we will primarily rely on survival analysis (i.e., event history modeling) to investigate if and when the event has occurred (Singer & Willett, 1993). For this study, the time scale for mortality will be recorded in discrete time intervals (i.e., baseline, one month, one year); therefore, the underlying continuous time-to-event process will be modeled using discrete time.

A major consideration will be the nested organization of the data. Patients (level-1) are nested within sites (level-2). When hierarchical data are analyzed without regard to the interdependence of the data type-I error rates are inflated (aggregation) or deflated (disaggregation) resulting in incorrect significance tests and invalid conclusions (Hox, 2002). While multilevel modeling methods explicitly account for the nested structure of data, this approach is not feasible because we do not have sufficient number of sites to treat these effects as random (Hox & Roberts, 2010; Roberts, Monaco, Stovall, & Foster, 2011). Therefore, each site will be evaluated for differences in multiple group analyses. If the site differences are trivial, we will collapse the data across sites (Little, 2013). Non-trivial differences will require a grouping variable for site in subsequent analyses.

**4.4.2. Analytic strategy.** Insights gained from the exploratory data analysis will then be used to fit appropriate statistical models to the data. Within the context of survival analyses, we will begin by modeling the unconditional model (no covariates) in order to establish a baseline model. Next, we will add covariates with time-varying (nonproportional hazard odds) effects. Using model constraints, we will then fit a proportional hazard odds model and compare. Finally, we will probe for hypothesized effects.

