### *Expected results*

We expect a standardized clinical protocol that selects patients for MCS based on shock severity, will be non-inferior with respect to 1 month and 1 year mortality compared to standard clinical protocols that do not differentiate based on shock severity in adult patients following an initial diagnosis of acute myocardial infarction complicated by cardiogenic shock (AMICS).

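### The 1-year hazard odds ratio in Hypothesis 1 is conditional on surviving the first month, so comparing it with 1.2 does not test the claimed non-inferiority on 1-year mortality

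*Protocol*

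**What the plan says.** Section 1.1 states that the severity-based protocol "will be non-inferior with respect to 1 month and 1 year mortality". The expected results under 4.4.2.1 repeat this: "will be non-inferior with respect to 1 month and 1 year mortality compared to standard clinical protocols". Section 4.1.1 fixes the primary endpoint: "The primary outcome variable will be 30-day all cause mortality". Section 4.1.2 lists "One year mortality" first among the key secondary outcomes.

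On the analysis, section 4.4.1 says "the time scale for mortality will be recorded in discrete time intervals (i.e., baseline, one month, one year". Section 4.4.2.1 then defines the "hazard probability for a given measurement occasion will be defined as the probability of mortality in that occasion, provided that patient is alive". It uses a logit link to describe "the effect of a particular covariate on the log hazard odds of mortality during a given time interval", and gives the coefficient for clinical protocol an occasion index. The decision rule is: "The assessment of non-inferiority will be performed by comparing hazard odds ratio confidence intervals to the non-inferiority margin", with the margin set at 1.2.

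Two other places bear on the point. Section 4.4.2 plans a proportional model, with one common hOR, as a comparison with the non-proportional one. The contingency paragraph of 4.4.2.1 brings in Kaplan–Meier failure rates, but only if the proposed models run into trouble.

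**The concern.** One-year mortality in the hypothesis means all deaths from the index event to one year. On the stated time grid, the hOR at the 1-year occasion describes something else: death between one month and one year among patients still alive at one month. Deaths in the first month do not enter it, and the groups compared are those left after any early difference has acted.

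The worked example in 4.4.2.1 makes the slip easy. It reads an hOR at 30 days as a ratio of the odds of having died by 30 days. That is right for the first interval, because every patient is at risk from baseline. Carried over to the 1-year occasion, the same reading is wrong, and the section does not say so.

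At stake is the second of the two conclusions in Hypothesis 1. The 1-year statement could be made when cumulative mortality lies beyond the margin, or withheld when it lies well inside.

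**Working it through.** **Inputs from the protocol.** Control 30-day mortality 39.7%; margin 1.2; total N 672; one-sided alpha 0.025; power 80% (4.4.2.1, Approach and Power).

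**Assumptions.** 1:1 allocation, so 336 per group. Control death rate from one month to one year among one-month survivors, h2 = 15%, with 5% to 25% as the range; the protocol gives no such figure. All ratios below are new protocol over standard protocol.

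**The plan's own figure.** Unpooled Z formula, bound 41.3% − 39.7% = 1.6 points, true difference 39.7% − 31% = 8.7 points in favour of the new protocol:

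n per group = (0.397×0.603 + 0.31×0.69) × (1.960 + 0.842)² / (0.016 + 0.087)² = 335.4, so 336 per group and 672 in total. The figure reproduces, but it concerns 30-day death only.

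**Formulas.** With h1 and h2 the interval hazards in one group, cumulative 1-year mortality is F = 1 − (1 − h1)(1 − h2). The interval odds ratio compares the h2 values; the cumulative odds ratio compares the F values. Control F = 1 − 0.603×0.85 = 48.7%.

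| Case (new protocol) | 30-day OR | 1-year-interval OR | New F | Cumulative 1-year OR |
|---|---|---|---|---|
| (a) 46% at 30 days, 15% later | 1.29 | 1.00 | 1 − 0.54×0.85 = 54.1% | 1.24 |
| (b) 44% at 30 days, 17% later | 1.19 | 1.16 | 1 − 0.56×0.83 = 53.5% | 1.21 |
| (c) 39.7% at 30 days, 18% later | 1.00 | 1.24 | 1 − 0.603×0.82 = 50.6% | 1.08 |

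In (a) the 1-year-interval hOR is below 1.2 while the cumulative ratio is above it. In (c) the order is reversed. Case (b) is below 1.2 in both intervals and only just above it cumulatively.

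**Sensitivity to h2.** For h2 from 5% to 25%, the cumulative odds ratio in (a) runs from 1.27 down to 1.21. Holding the interval odds ratio of (c) at 1.24, its cumulative odds ratio runs from 1.03 to 1.11.

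**With the confidence-interval rule.** In (a), expected one-month survivors are 336×0.54 = 181 (new) and 336×0.603 = 203 (control). Expected later deaths are 27.2 and 30.4, leaving 154.2 and 172.2 survivors. The standard error of the log odds ratio is √(1/27.2 + 1/154.2 + 1/30.4 + 1/172.2) = 0.286, and the 95% upper limit is exp(1.96×0.286) = 1.75. At its expected value, (a) therefore does not pass on the upper limit; its chance of passing is about 9%. In (b) the upper limits are about 1.62 and 2.00.

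**A stronger counterexample.** Take an hOR of 1.5 to 30 days and 0.8 afterwards. Then h1 = 49.7%, h2 = 12.4% and F = 55.9% against 48.7%: 7.2 points, about 24 more deaths per 336, cumulative odds ratio 1.33. In 200,000 simulated trials of 336 per group:

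| Rule | 1-year-interval hOR | Cumulative 1-year OR |
|---|---|---|
| Point estimate below 1.2 | 91% | 25% |
| 95% upper limit below 1.2 | 25% | 0.4% |

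For h2 from 10% to 20%, the upper-limit rule passes in 18% to 31% of trials on the interval hOR and in 0.2% to 0.7% on cumulative mortality.

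**If both intervals had to pass.** An hOR of exactly 1.2 in each gives a cumulative odds ratio of 1.21 to 1.24 over h2 from 5% to 25%, so the gap is small. A common proportional hOR in the stronger counterexample would be about 1.32 and would not pass.

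**The case against.** The strongest reply is that the trial's main conclusion is untouched. The primary endpoint and the power calculation concern 30-day death, where the first-interval hOR does reflect total mortality. This stands, and it limits the severity.

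Second, case (a) would exceed 1.2 on the 30-day odds ratio (1.29), so a reader of the whole result would see the early harm. This also stands: large false passes need early harm. But the protocol does not say that both time points must pass, and case (c) errs the other way with no 30-day difference.

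Third, the section does not say that the second-interval hOR alone decides the 1-year claim, and a common hOR is also planned. That is true, but the common hOR is fitted only for comparison and would give no separate 1-year result. Whichever hOR is used, the main analysis contains no test of cumulative 1-year mortality. The Kaplan–Meier route is cumulative but reserved for model failure, so the main and fallback analyses would answer different 1-year questions.

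Fourth, the choice could be left to the statistical analysis plan. But the protocol itself fixes the hazard definition, the model and the comparison with 1.2, so the mismatch lies in what it states.

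A reader might infer that the plan readily passes a protocol with more deaths. The documents do not support that: any non-inferiority margin allows some excess, and under the confidence-interval rule (a) would usually fail. Nor do they show that most deaths by one year fall before day 30; that follows only from an assumed later rate.

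**Conclusion.** The point holds for the 1-year part of Hypothesis 1. The hOR at the 1-year occasion is conditional on one-month survival and is not a 1-year mortality ratio, so the 1-year non-inferiority claim does not follow from it. With 15% later deaths assumed in controls, the interval and cumulative odds ratios fall on opposite sides of 1.2 in both directions: 1.00 against 1.24, and 1.24 against 1.08. These are point estimates. Under the confidence-interval rule, and assuming 336 per group, false passes are less frequent and depend on early harm; they would largely disappear if both intervals had to pass. The existence of the mismatch needs no assumption, but its size depends on the later death rate and on 1:1 allocation.

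It should be fixed because it affects a secondary conclusion. It is not a must-fix defect, and it does not put the 30-day comparison in doubt.

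**What to change.** In section 4.4.2.1, state that 1-year non-inferiority is judged on cumulative 1-year mortality, derived from the model already planned as 1 − (1 − h1)(1 − h2) in each group. Give the between-group contrast a delta-method or bootstrap confidence interval and compare it with a margin stated on that cumulative scale. The margin should be set deliberately, since an hOR of 1.2 in each interval corresponds to a cumulative odds ratio slightly above 1.2. Report the one-month-to-one-year hOR only as a landmark result among 30-day survivors, and do not label it 1-year mortality.

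The cost is one or two sentences and one derived quantity, with no new data.

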**Confidential**

The information provided in this document is strictly confidential and is intended solely for the guidance of the clinical investigation. Reproduction or disclosure of this document whether in part or in full to parties not associated with the clinical investigation, or its use for any other purpose, without the prior written consent of the Principal Investigator is not permitted.

Throughout this document, symbols indicating proprietary names (®, TM) are not displayed. Hence, the appearance of product names without these symbols does not imply that these names are not protected.

*Version 2 / Date 05/08/2020*

PROTOCOL SUMMARY	
Study Title	Carolinas Cardiogenic Shock Initiative
Study Design	This is a case series and prospective patient registry
Study Objectives	To determine if deferred or delayed implantation of Impella device based on shock severity index is non-inferior with respect to 1 month and 1 year mortality compared to standard clinical protocols that do not differentiate based on shock severity in adult patients following an initial diagnosis of acute myocardial infarction complicated by cardiogenic shock (AMICS).
Study Population	The registry will include all eligible subjects from approximately 5/1/2019 until 4/30/2024, at participating sites.
Study Procedures	Adult patients with a diagnosis of AMICS will have their clinically available data contribute to the project registry. Patients who meet criteria for inclusion into the registry will have their chart reviewed periodically for the purposes of the registry, for proof of survival at one month and one year post-admission. Social Security Death Index (SSDI) data will be used to determine mortality at one month and one year if unable to confirm using the electronic health record. Patient clinical data will be pulled from the medical record and entered or migrated into a database for comparison and analysis. All data collected for the study will originate in the medical record from clinically available information, from a national death database, or from other publically available data sources.

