## 4. INVESTIGATIONAL PLAN

### 4.1 Overall Study Design

The Carolinas Cardiogenic Shock Initiative is a clinical pathway and process improvement protocol already agreed upon by participating sites, to improve care by using a standardized algorithm to treat patients with AMI and CS. This prospective registry will capture data from this protocol as a multi-site research project in parallel with this standardized non-research clinic workflow protocol. Participating providers will follow the clinical protocol as standard of care for AMICS patients, as clinically appropriate. Patients who have been admitted and diagnosed with AMICS and meet all eligibility criteria will have their data entered in this registry.

All eligible patients will be entered into the registry and follow-up via the EMR and/or SSDI will occur at 30 days and one year to assess mortality. No additional provider appointments or further testing will be required as a part of this Registry, other than what each provider feels is medically necessary and indicated as a part of the patients' care plan.

Treatment decisions and timing will follow an approved clinical protocol and algorithm (see Appendix A) based on shock severity classification. The research team at each site will capture data generated during standard of care lab tests and clinical procedures, as well as data collected during clinical visits from eligible patients. Our target accrual is approximately 672 patients, cumulative across all participating sites.

Many of the patient specific outcomes and variables of interest for this study, are already submitted to the National Cardiovascular Data Registry (NCDR). Some additional data elements, as described in Appendix C, will also be captured. There are no benefits in participation other than the scientific knowledge gained, and the only alternative to participation is not participating.

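### Hypothesis 1 compares two clinical protocols, but no source is given for the typical-protocol group, and the site rule defeats the comparison if that group comes from separate sites

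*Protocol*

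**What the plan says.** **The test.** Section 4.4.2.1 (Hypothesis 1, Approach) fits a discrete-time survival model with a logit link. The covariate of interest is clinical protocol, illustrated as "if clinical protocol is coded 1 for typical and 0 for being based on a shock severity score". Non-inferiority is judged on its hazard odds ratio against 1.2. The Power paragraph plans 672 patients and names a control and a treatment group.

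**The patients.** The Protocol Summary describes a case series and registry: "The registry will include all eligible subjects from approximately 5/1/2019 until 4/30/2024, at participating sites". Section 4.1 calls the shock-severity pathway "a clinical pathway and process improvement protocol already agreed upon by participating sites" and adds: "Participating providers will follow the clinical protocol as standard of care for AMICS patients, as clinically appropriate". The accrual target of about 672 is cumulative over those same sites.

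**The site rule.** Section 4.4.1 rules out random site effects because there are too few sites. Two outcomes remain: "If the site differences are trivial, we will collapse the data across sites", or "Non-trivial differences will require a grouping variable for site in subsequent analyses". The Missing Data paragraph mentions "chi-square difference tests to evaluate site-level difference". No threshold separates trivial from non-trivial, and Hypothesis 1 is not exempted from the rule.

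**The concern.** The exposure is a policy adopted by a whole site, not something that differs between patients at one site. Leave for individual clinical judgement permits deviations from the algorithm, but it does not create a group treated under a typical protocol. Two problems follow.

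First, if every registry site follows the algorithm, there is nothing to compare and the primary hypothesis has no estimable quantity.

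Second, suppose the missing group is supplied by other sites. The site rule then works against the test. A real protocol effect would itself appear as a difference between sites, and so could trigger the site term that absorbs it. If the software resolved the dependency by dropping a site indicator, the coefficient labelled as protocol could become a contrast between two arbitrary sites. If sites were collapsed instead, protocol would be fully confounded with site.

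At stake is whether the registry can give any interpretable answer to Hypothesis 1.

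**Working it through.** **Step 1. Reproduce the planned sample size.** Inputs from the Power paragraph of 4.4.2.1: control mortality 0.397, limit 0.413, true treatment mortality 0.31, one-sided alpha 0.025, power 80%, unpooled Z test. Equal allocation is assumed.

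n per group = (z₀.₉₇₅ + z₀.₈₀)² × [p_C(1−p_C) + p_T(1−p_T)] / (limit − p_T)²

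= 7.849 × (0.2394 + 0.2139) / 0.103² = 7.849 × 0.4533 / 0.010609 = 335.4, rounded up to 336, or 672 in total.

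Power at 336 per group: SE = √(0.4533/336) = 0.0367, and Φ(0.103/0.0367 − 1.96) = 80.07%.

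The stated figure is correct as arithmetic. It needs two groups of 336, whereas Section 4.1 accrues all 672 at sites following one protocol.

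**Step 2. Information on the protocol covariate.** Let x be protocol, q the overall share of patients with x = 1, and q_s that share at site s with n_s patients. The residual sum of squares of x, given the other columns of the design, is:

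- without a site term: N q(1−q);
- with fixed site groups: Σ n_s q_s(1−q_s).

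If this is zero, the coefficient cannot be estimated. With fixed site groups it is zero whenever each q_s is 0 or 1. The number of sites is not stated, so 2, 4, 6 and 8 equal sites were tried with N = 672, and with half the patients at x = 1 in cases B and C. Results for four sites:

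| Source of typical-protocol patients | No site term: columns / rank / information | Fixed site groups: columns / rank / information |
|---|---|---|
| A. None; all sites x = 0 | 2 / 1 / 0 | 5 / 4 / 0 |
| B. Separate sites | 2 / 2 / 168 | 5 / 4 / 0 |
| C. Same sites before adoption | 2 / 2 / 168 | 5 / 5 / 168 |

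The value 168 is 672 × 0.5 × 0.5. The pattern is the same for 2, 6 and 8 sites. A model with sites as multiple groups gives the same answer in A and B, because x is constant within every group.

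**Step 3. Which case the protocol describes.** The Protocol Summary and Section 4.1 together describe case A. No passage names comparator sites (B), and no passage names an earlier cohort or gives an adoption date (C).

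**Step 4. Can the protocol effect trigger the site rule in case B?** An illustrative simulation used 20,000 runs, 672 patients, equal sites, half of them on each protocol, no other site differences, and a chi-square test of equal site mortality at 0.05:

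| Mortality by protocol | 4 sites | 6 sites | 10 sites |
|---|---|---|---|
| 39.7% vs 31% (planning values) | 48% | 41% | 31% |
| 39.7% vs 56.8% (odds ratio 2.0) | 98% | 95% | 90% |

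Entries are the proportion of trials in which the protocol effect alone makes the site check reject. The site count, the split of protocols by site and the 0.05 trigger are all assumptions. The odds ratio of 2.0 is only the protocol's example for explaining the coding.

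**The case against.** The strongest objection is that collinearity with site presupposes a design the protocol does not describe. A reader might infer that some sites run the typical protocol and others the shock-severity protocol, so that the site variable is what destroys the ratio. No passage says so. On the literal text the ratio is already lost without a site term, and with a pre-adoption comparator at the same sites the collinearity disappears. This objection stands, and it limits the site-rule problem to case B.

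A reader might also take the simulated percentages as properties of this trial. They are not. Section 4.4.1 sets no 0.05 trigger, and the Missing Data paragraph mentions chi-square difference tests without a threshold.

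Third, 4.4.2.1 has a fallback for unforeseen modelling problems: logistic regression, with non-inferiority from a z statistic on Kaplan–Meier failure rates. No site term is stated for it. In case B it would give an answer, so it is too strong to say that no answer could ever be produced. But that answer would be confounded with site, and the fallback needs a comparator group too, so it does not help in case A.

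Finally, the exact form of a site term is often left to the SAP. That does not dispose of the point. The protocol itself fixes the exposure, the accrual source, the conditional site variable and the exclusion of random site effects, and these do not fit together.

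**Conclusion.** The concern holds in a conditional form. The root defect is that the protocol gives no source for the typical-protocol group that Hypothesis 1 and the power calculation require.

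- **As written (case A):** the protocol covariate does not vary and the ratio is not estimable, with or without a site term.
- **Separate comparator sites (case B):** the ratio is not estimable once site enters as fixed groups, and is confounded with site if sites are collapsed.
- **Same sites before adoption (case C):** the ratio is estimable with site included, but protocol is aligned with calendar time.

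The zero-information results in A and B are exact and do not depend on the number of sites. They rest on reading exposure as constant within each site during the registry period, which follows from Section 4.1. How often the site rule would be triggered cannot be determined from the protocol. The figure of 672 is not itself in error.

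**What to change.** In Sections 4.1 and 4.4.2.1, name the source of the comparator patients. In Section 4.4.1, set a site rule to match:

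1. **Separate comparator sites.** Assess site differences within protocol group, with the protocol term in the model. Do not enter site as fixed groups for Hypothesis 1. Base the confidence limit for the 1.2 comparison on between-site variation, with a small-sample correction whose degrees of freedom allow for any site-level covariates. Report the result as a between-site comparison.
2. **Same sites before adoption.** Keep site as a fixed effect and address calendar time explicitly, for example through admission date.
3. **No concurrent or historical comparator.** Restate Hypothesis 1 as a comparison with an external rate, or as descriptive.

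Changing the site rule alone is not enough, because under the present text the covariate would still have no variation.

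The cost is wording in these sections. Under the first option the interval will be wider, since it rests on few sites, and the stated 80% power will look less favourable.
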